## 2. INTRODUCTION

### 2.1. Background

Xgene Pharmaceutical has developed XG005, a prodrug conjugating pregabalin, an anti-hyperalgesic, antialloodynic, and analgesic, with naproxen, an analgesic and anti-inflammatory agent. It is the first in a new class of “dual-acting” conjugate analgesics that has been engineered to reduce the gastrointestinal (GI) safety risks associated with naproxen and improve clinical efficacy in the treatment of acute and chronic pain. XG005 has been evaluated in preclinical and Phase 1 clinical studies. In the first Phase 1 study in healthy volunteers, oral XG005-01 (capsule formulation) demonstrated an acceptable safety profile with no additional adverse events compared with pregabalin or naproxen (parent drugs). Xgene Pharmaceutical has since developed an improved tablet formulation (XG005) which showed improved bioavailability for pregabalin and naproxen. In two Phase 1 single and multiple ascending dose studies with XG005 tablet formulation, a clinically relevant dose range was evaluated in healthy volunteers. These studies showed a safety profile consistent with pregabalin and naproxen.

In general, pain symptoms are classified into two broad mechanism-based pain categories: tissue-injury pain (nociceptive) or nervous-system-injury pain (neuropathic). Some of the chronic pain, such as the low back pain or moderate to severe arthritis pain, have been shown to be the result of neuropathic as well as nociceptive pain mechanisms. It has been demonstrated that the analgesic effects can be enhanced by co-administration of gamma-aminobutyric acid (GABA) analogs, such as pregabalin or its predecessor gabapentin together with non-steroidal anti-inflammatory drugs (NSAIDs) (Yu et al. 2011; Corleto et al. 2014; Banoob et al. 2002; Petroski 1993; Van Gossuet et al. 1993; D'Haens et al. 1993; Ivey et al. 1980). They can interact in a synergistic or additive manner to control pain in the preclinical animal models as well as in the clinical practices. The synergy of these two classes of drugs can potentially allow a reduction in the dose required of each compound, leading to a reduction in the side effects, and the enhancement of the clinical utility of these compounds. Furthermore, combining the prodrug strategy and the potential complimentary synergy between the two drugs may lead to an optimal clinical outcome in terms of improved clinical efficacy and reduced GI events in patients with chronic pain.

### 2.2. Unmet Medical Need

Both acute and chronic pain remain as high unmet medical needs with high global burden of disease (Enright et al. 2016; Blyth et al. 2019). Acute pain is the most common reason for visiting an emergency department, and surgical procedures are associated with acute postoperative pain (Sinatra 2010). Chronic pain causes significant suffering as indicated by the Global Health Burden of Disease survey demonstrating that headache and low back pain were the leading causes of years lived with disability (GBD 2017).

Multimodal approaches are used for the treatment of pain for both inflammatory and neuropathic pain conditions to limit the use of opioid analgesics (Finnerup 2019). There remains a significant unmet medical need for treatment of chronic pain with non-opioid drugs that are safe and tolerable. In an effort to develop a better analgesic to address these needs, Xgene Pharmaceutical

has designed an orally bioavailable “dual-acting” prodrug conjugating two well-established analgesics with different mechanisms of action: naproxen and pregabalin conjugated with a linker that has been previously approved in a product Horizant® ([Horizant \[pregabalin\] 2013](#)).

Non-steroidal anti-inflammatory drugs (NSAIDs) are widely used for the management of pain. Naproxen, a cyclo-oxygenase inhibitor, is a potent inhibitor of prostaglandin synthesis. It is one of the most prescribed NSAIDs in the world, available over the counter, for the treatment of pain and inflammation and has the most favorable cardiovascular side effect profile in this class ([Naprosyn 2017](#); [Trelle et al. 2011](#); [Coxib and traditional NSAID Trialists’ \(CNT\) Collaboration et al. 2013](#); [Inza 2019](#)).

Pregabalin is structurally related to the naturally occurring amino acids L-leucine and gamma-aminobutyric acid (GABA). Pregabalin was approved in 2004 to manage peripheral neuropathic pain, fibromyalgia in adults ([Lyrica 2013](#)) and is now available as a generic drug. The dose range in humans is 150 to 600 mg per day. Pregabalin binds to the alpha2-delta protein, an auxiliary subunit protein of voltage-gated calcium channels with high affinity ( $IC_{50} = 37\text{ nM}$ ), which is required for its pharmacology. The (R)-enantiomer of pregabalin was 10-fold less potent than its (S)-enantiomer ([Lyrica 2013](#)).

XG005 is intended for use in both acute and chronic pain conditions. Due to the unique mechanism of action of this prodrug on both neuropathic and inflammatory mechanisms of pain, it is expected to have a better benefit in pain management than currently available medications and reduce the use of potentially more harmful drugs such as opioids.

### **2.3. XG005 Clinical Experience in Healthy Subjects**

Xgene Pharmaceutical has completed a Phase 1 single-ascending dose (SAD) study (XG005-01; capsule formulation) and a Phase 1 SAD/multiple ascending dose (MAD) study (XG005; tablet formulation) in healthy subjects at clinical sites in Australia.

#### Study XG005-01

The completed Phase 1 SAD study in 40 healthy subjects demonstrated that area under the plasma concentration-time curve from time 0 to the last quantifiable point ( $AUC_{0-t}$ ) of naproxen and pregabalin increased with dose level of XG005-01 across the dose range 50 mg to 1000 mg, with the increase being linear with dose for naproxen but less than dose proportional for pregabalin. There was no dose or treatment-related trend in the incidence of treatment-emergent adverse events (TEAEs; defined as adverse events reported after treatment was received) for subjects who received XG005 compared with subjects who received placebo. Most TEAEs reported during this study were mild in intensity, none was severe. The most commonly reported adverse event was dizziness in 8 of 30 subjects (27%). No deaths, serious adverse events (SAEs) or TEAEs leading to study withdrawal were reported.

#### Study XG005-02

The second Phase 1 study (XG005-02; NCT04067947) evaluated safety, tolerability, and PK profile of XG005 (tablet formulation) in 32 healthy volunteers in each SAD and MAD cohorts. XG005 was evaluated at the doses of 250, 500, 1000, 1250 mg in the single dose and twice-a-day

(BID) dose up to 7 days. Following single and multiple dose administration of XG005, AUCs and maximum concentration in plasma ( $C_{max}$ ) of XG005, naproxen, and pregabalin increased in a dose proportional manner. There was no dose or treatment-related trend in the incidence of TEAEs for subjects who received XG005 compared with subjects who received placebo. Most TEAEs reported during this study were mild in intensity, none was severe. The most commonly reported adverse event (AE) was dizziness (9 [37.5%] of 24 XG005 subjects) in the SAD cohort, and somnolence (7 [29.17%] of 24 XG005 subjects) in the MAD cohort. In comparison, in the LYRICA controlled trials in adult patients, dizziness was experienced by 30% of LYRICA-treated patients and somnolence was experienced by 23% of LYRICA-treated patients ([Lyrica 2013](#)). No deaths or SAEs were reported during this study. None of the subjects in XG005 groups discontinued study drug due to TEAEs.

#### Study XG005-02-PK-02

This Phase 1 bridging MAD study in Chinese healthy volunteers enrolled 16 subjects. 8 subjects were administered 750 mg or 1250 mg XG005 BID for 6.5 days, respectively, following titration to target dose levels. All subjects had good tolerance to study drug. No new drug-related TEAEs other than those known for naproxen or pregabalin. Notable TEAEs were dizziness, somnolence, constipation, and oral ulcer. But all were mild in severity and no subject discontinued from the study.

The Investigator's Brochure summarizes the nonclinical and clinical experience with XG005, naproxen, and pregabalin ([XG005 IB 2022](#)). Additional efficacy and safety information for the marketed products can be found in the package insert for naproxen ([Naprosyn 2017](#)) and pregabalin ([Lyrica 2013](#)).

#### **2.4. Study Rationale**

XG005 is being developed for the management of pain. Pre-clinical animal models have demonstrated improved efficacy for pain and inflammation compared with naproxen alone ([Hurley et al. 2002](#)), and pilot human studies have shown that both pregabalin and naproxen could reduce pain in a bunionectomy model with a possible synergistic effect ([Wang et al 2010](#)). By targeting both neuropathic and inflammatory aspects of pain in a single prodrug, therapeutic advantages are expected. With the use of this conjugate approach, there is a potential for a better benefit risk profile compared with available drugs, with lowered use of opiates.

This study will evaluate the safety, efficacy, and PK of low dose (750 mg) and high-dose (1250 mg) XG005 oral tablets compared with placebo in subjects undergoing bunionectomy.

### 3. OBJECTIVES AND ENDPOINTS

Objectives	Endpoints
Primary Efficacy:	

 
To evaluate the efficacy of high dose XG005 [1250 mg Q12] compared to placebo for pain control in subjects undergoing bunionectomy.
 
	
 
Summed pain intensity from end of surgery to 48 hours post-surgery (SPI48) for high dose XG005 vs placebo
 

Secondary Efficacy:	

 
To evaluate the efficacy of low dose XG005 [750 mg Q12] compared to placebo for pain control in subjects undergoing bunionectomy.
 
To evaluate high and low dose XG005 compared to placebo for total rescue consumption and time to first use from end of surgery.
 
To evaluate high and low dose XG005 compared to placebo for PGA
 
To evaluate high and low dose XG005 compared to placebo for postoperative nausea.
 
To evaluate the efficacy of high dose XG005 compared to low dose XG005 for pain control in subjects undergoing bunionectomy
 
	
Key Secondary Endpoints:
 
 
SPI48: low dose XG005 vs placebo
 
Total tramadol rescue medication consumption in MEQs over 48 hours: high dose XG005 vs placebo
 
Total tramadol rescue medication consumption in MEQs over 48 hours: low dose XG005 vs placebo
 
 
Additional Analgesic Endpoints:
 
 
Time to first use of rescue medication from end of surgery: high dose XG005 vs placebo
 
Time to first use of rescue medication from end of surgery: low dose XG005 vs placebo
 
PGA at 48 hours: high dose XG005 vs placebo
 
PGA at 48 hours: low dose XG005 vs placebo
 
Cumulative nausea (NNRS) assessment scores through 24 hours: high dose XG005 vs placebo
 
Cumulative Nausea (NNRS) assessment scores through 24 hours: low dose XG005 vs placebo
 
SPI48: high dose XG005 vs low dose XG005
 

Tertiary Efficacy (All Treatment Arms):	

 
To evaluate rescue medication consumption at 24, 48, and 72 hours, time to first use of rescue medication from end of surgery, and proportion of subjects requiring rescue medication.
 
To evaluate nausea assessment scores at various timepoints.
 
To evaluate high and low dose XG005 compared to placebo for SIS
 
	
 
Total oral opioid rescue medication consumption at 24, 48, and 72 hours
 
Nausea (NNRS) assessment scores at 1, 4, 8, 12, 24, 48, 72 hours
 
SPI at 0, 1, 2, 3, 4, 6, 8, 10, 12, 16, 20, 24, 30, 36, 42, 48, 54, 60, 66, and 72 hours
 
Pain intensity at various timepoints
 
SIS at 24, 48 and 72 hours
 
Percentage of subjects requiring rescue at various timepoints
 
PGA of pain control at various timepoints
 
Ramsay Sedation Scale at various timepoints
 

Objectives	Endpoints

 
Exploratory purposes only: To estimate subject's potential placebo response by use of a pre-study personality questionnaire at Screening.
 
	
 
Estimated of subject susceptibility to placebo response at Screening using a pre-study personality questionnaire
 

Safety:	

 
To evaluate the safety and tolerability of XG005 in a perioperative population
 
	
Safety and tolerability of XG005 compared with placebo measured:
 
 
The incidence, intensity, relationship, and seriousness of TEAEs by treatment group.
 
The number and percentage of premature withdrawals due to AEs in each treatment group.
 
Treatment-emergent changes in vital signs (blood pressure, heart rate, body temperature, respiratory rate, continuous pulse oximetry) and Sp02 after each Treatment Period dose and the Follow-up Visit compared to Baseline values.
 
Treatment-emergent changes in clinical laboratory tests and ECGs compared to Baseline.
 

Pharmacokinetics	

 
To investigate the PK of XG005, naproxen, and pregabalin in a perioperative population
 
	
 
Area under the plasma concentration-time curve from time zero to time <math>t</math> of the last measured concentration above the limit of quantification (AUC0-last)
 
Area under the plasma concentration-time curve from zero to infinity (AUC0-inf)
 
Maximum plasma concentration (Cmax)
 
Trough plasma concentration prior to each dose (Ctrough)
 
Time to reach maximum plasma concentration (Tmax)
 
Terminal elimination rate constant (<math>\lambda_z</math>) with the respective half-life (t1/2).
 

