## 1.2. Schedule of Assessments

Assessment	Screen	Day 1: Surgery		Treatment Period (Hours Post End of Surgery)											End of Study/Early Termination v
	Days -28 to -1	Pre-Surgery a	Surgery	0	1	2	4	8	12	24	36	48	60	72	
Written Informed Consent b	X														
Inclusion/Exclusion Criteria c	X	X													
Medical History	X	X													
Physical Examination d	X														
Vital Signs e	X	X		X	X	X	X	X	X	X	X	X	X	X	X
Electrocardiogram f	X														X
Clinical Laboratory Testing g	X													X	X
Pregnancy Test h	X	X													X
Urine Drug Screen g	X														
COVID-19 test w	X	X w													
Adverse Events Monitoring i	←————→														
Prior/Concomitant Medications	←————→														
Pre-study personality questionnaire j	X														
C-SSRS Baseline/Screening Version Appendix J	X														

	Screen	Day 1: Surgery		Treatment Period (Hours Post End of Surgery)												End of Study/Early Termination v			
Assessment	Days -28 to -1	Pre-Surgery a	Surgery	0	1	2	4	8	12	24	36	48	60	72	Clinic Visit, Day 15 ( $\pm 2$ )				
C-SSRS Since Last Visit Version Appendix K															X	X			
Patient Health Questionnaire-9 (PHQ-9)	X																		
General Anxiety Disorder (GAD-7)	X																		
Domiciled in Clinic																			
Enrollment/ Randomization		X																	
Study Drug Dosing (XG005 or Placebo) k		X 60 min prior to surgery		Every 12 hours after the first dose defined as "Time 0" for dosing purposes only															
Blood Sample for Pharmacokinetic Assessment l		X Pre-dose			Drawn at 1, 2, 3, 4, 6, 8, 10, 12, 24, 30, 36, 42, 48, 54, 60, 66, and 72 hours ( $\pm 15$ min window) after the end of surgery (last suture) 														
Anesthesia and Bunionectomy Surgery m			X																
Continuous Pulse Oximetry n									X	X	X	X	X	X					
Rescue Medication				PRN															
Numeric Pain Rating Scale (NPRS) p,q					Measure at 0, 1, 2, 3, 4, 6, 8, 10, 12, 16, 20, 24, 30, 36, 42, 48, 54, 60, 66, and 72 hours after the end of surgery ( $\pm 10$ min window)														X (ET only)
Patient Global Assessment (PGA) of Pain Control r										X		X		X			X (ET only)		

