- e) Vital signs (blood pressure [systolic/diastolic], heart rate, respiratory rate, oral body temperature) will be collected from all subjects at Screening, before the first dose Pre-Surgery ( $\pm 10$  minutes) and Hours 0, 1, 2, 4, 8, 12, 24, 36, 48, 60, and 72, and Day 15/Early Termination ( $\pm 10$  minutes). Monitoring of continuous pulse oximetry begins at Hour 0 (start of the domiciling period). Vital signs may be obtained at any other times as deemed necessary by the Investigator. Vital signs throughout the study should be obtained supine after resting for approximately 5 minutes. Automated blood pressure machines may be used to standardize measurements. Body temperature will be determined by obtaining oral temperature ( $^{\circ}$ C).
- f) 12-lead ECG data will be collected from all subjects at Screening and at the Day 14 clinic visit, and from any subject who is determined to be exhibiting any relevant abnormality per the discretion of the investigator. 12-lead ECGs will be obtained at each time point using an ECG machine that automatically calculates the heart rate and measures PR, QRS, QT, and QTc intervals. QTcF will also be calculated. 12-lead ECGs will be measured in the supine position, after the subject has been supine for at least 10 minutes.
- g) Clinical laboratory parameters include standard **chemistry** (albumin, total bilirubin, total protein, calcium, alkaline phosphatase, alanine aminotransferase [ALT], aspartate aminotransferase [AST], blood urea nitrogen [BUN], creatinine, glucose, sodium, potassium, chloride, bicarbonate, lactate dehydrogenase

[LDH], and uric acid; **hematology** (HbA1c [Screening only], hemoglobin, hematocrit, red blood cell [RBC] count, RBC indices, mean corpuscular hemoglobin [MCH], mean corpuscular hemoglobin concentration [MCHC], platelet count, and white blood cell [WBC] count including differential; coagulation panel (prothrombin time [PT], partial thromboplastin time [PTT], and fibrinogen); **serology** (human immunodeficiency virus [HIV] antibody, hepatitis B virus surface antigen, hepatitis B anti-core antibody (anti-HBc) and anti-surface antibody, and hepatitis C virus antibody); **urinalysis** (pH, specific gravity, blood and leukocyte esterase, glucose, protein, and ketones), and **urine drug screen** (amphetamines, barbiturates, benzodiazepines, cocaine, opiates, phencyclidine [PCP], tetrahydrocannabinol [THC], methamphetamine, methadone, and ecstasy).

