- h) For premenopausal women, a serum pregnancy test will be conducted at Screening visit, a urine pregnancy test will be conducted pre-surgery on Day 1 and at Exit Visit. Premenopausal women must have a negative serum pregnancy test to be included in study. Results must be available before surgery.
- i) Reporting of treatment-emergent AEs begins at the time of first dose of study drug and ends 30 days after the last dose of study drug. Non-treatment emergent AE reporting begins at Screening after signing of ICF until the first dose of study drug is administered.
- j) Subjects will be assessed at Screening on their potential placebo response by use of a pre-study personality questionnaire ([Appendix B](#)). This is a exploratory analysis for information purposes only.
- k) Study drug will be administered 60 minutes prior to start of surgery and every 12 hours for 72 hours after the time of first dose. The clock time of first dose is noted as “Time 0”, and it will be recorded to facilitate the PK analyses.
- l) Blood draws will always be performed after NPRS assessment and prior to the first administration of rescue medication. Considering the surgery time may largely vary among subjects, the PK sampling plan used the post-end-of-surgery schedule to be consistent with the efficacy assessment schedule. Each subject in the PK group (one site only) will have blood samples collected for PK assessments at predose and at the following intervals post-surgery (last suture) 1, 2, 3, 4, 6, 8, 10, 12, 24, 30, 36, 42, 48, 54, 60, 66, and 72 hours ( $\pm 15$  min window). XG005, naproxen, and pregabalin concentrations in plasma will be measured. The actual clock time when the PK sample is collected will be recorded, and the post-dose time for PK analysis will be calculated based on the recorded clock time. All subjects will have blood samples collected for PK assessments at any time in which a subject is determined to be exhibiting any relevant abnormality per the discretion of the investigator.
- m) Subjects will undergo primary, unilateral, first metatarsal Austin bunionectomy. The surgical procedure should be limited to a maximum duration of 90 minutes. End of surgery will be defined as completion of the last suture.
- n) Subjects will be on continuous pulse oximetry monitoring throughout the confinement period but, absent a respiratory AE, oxygen saturation ( $SpO_2$ ) will be recorded every 12 hours post-end of surgery.

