#### 4.2. Scientific Rationale for Study Design

Preemptive administration of analgesic medication is more effective than medication given after the onset of the painful stimulus ([Error! Reference source not found.](#); [Error! Reference source not found.](#); [Ménigaux C](#), Adam F, Guignard B, Sessler DI, Chauvin M. Preoperative gabapentin decreases anxiety and improves early functional recovery from knee surgery. *Anesth Analg*. 2005;100:1394–9.). It has been suggested that the treatment before or during surgery prevents or alleviates the formation of peripheral and/or central sensitization which may reduce the development of pain for some time after surgery. In the current study, we included both preoperative and postoperative dosing to achieve maximal “preventive” analgesia that covers a wider window of opportunity to inhibit the formation of peripheral/central sensitization and treat postsurgical pain. In addition, by dosing preoperatively, it makes  $T_{max}$  match the time of anticipated onset of pain. Furthermore, the efficacy of pre- and post-operative pain relief using the combination of naproxen and pregabalin after bunionectomy surgery has been reported ([Wang et al 2010](#)). The present study is a double-blind, placebo-controlled randomized trial of preemptive analgesia with XG005, a prodrug of naproxen and pregabalin in adult patients.

The three Phase-I studies showed favorable PK characteristics of naproxen and pregabalin following administration of XG005, in particular, the  $C_{max}$  of both naproxen and pregabalin occur simultaneously following oral administration of XG005, with  $T_{max}$  at approximately 4 hours. This PK characteristic may result in simultaneous onset of drug effects (additive or synergistic) of naproxen and pregabalin that offers a great pharmacological benefit to clinical needs for acute pain treatment. Since the pain-relieving efficacy of XG005 is solely associated with the systemic exposure of naproxen and pregabalin resulted from the XG005 absorption and subsequent hydrolysis, the dose selection for XG005 in the current study is based on the considerations to match the systemic exposures of an efficacious naproxen dose and pregabalin dose. The steady status  $C_{max}$  for naproxen and pregabalin resulted from XG005 oral dosing was lower than the  $C_{max}$  from combined dosing of naproxen and pregabalin, which may indicate potential advantage on reducing side effects from each drug when dosed combined.

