### 8.2. Safety Assessments

The timing and frequency of all safety assessments are provided in the SOA ([Section 1.2](#)). Safety endpoints include monitoring and recording of AEs and SAEs, clinical laboratory results (serum chemistry, hematology, coagulation, and urinalysis), 12-lead ECG results, and vital signs measurements (blood pressure [systolic and diastolic], heart rate, respiratory rate, oral body temperature, and continuous pulse oximetry), and recording of relevant safety data.

Trained staff on hand in the research unit will monitor respiratory safety via respiration rate, continuous pulse oximetry and oxygen saturation ( $\text{SpO}_2$ ) checks every 12 hours post-end of surgery within a  $\pm 10$ -minute window, and somnolence if observed by Staff at times other than

when a formal assessment of somnolence is scheduled. The Ramsay Sedation Scale (RSS, [Appendix G](#)) will be used as an assessment of sedation (somnolence) with the same time sequence as the NPRS determination, but with a window of  $\pm 15$  minutes. A Columbia-Suicide Severity Rating Scale since last visit ([Appendix K](#)) will be administered at 72 hours post treatment and at the follow-up visit and at the end of study visit/early termination visit.

For all safety assessments, the investigator will determine whether results are clinically significant, which is defined as any variation in a result that has medical relevance and that may result in an alteration in medical care (e.g., active observation, diagnostic measures, or therapeutic measures). If clinical significance is noted, the result and reason for significance will be documented and an AE reported on the AE page of the subject's electronic case report form (eCRF). The investigator will monitor the subject until the result has reached the reference range or the result at Screening, or until the investigator determines that follow-up is no longer medically necessary.

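### The SpO2 safety endpoint needs a baseline, a value after every dose and a follow-up value, but the operative schedule records SpO2 only 12-hourly from Hour 12 and other sections conflict with it

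*Combined protocol and SAP*

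**What the plan says.** Section 3 (Objectives and Endpoints, Safety) sets an endpoint of treatment-emergent change in vital signs, with continuous pulse oximetry inside the vital-signs parenthesis, and in SpO2, "after each Treatment Period dose and the Follow-up Visit compared to Baseline values".

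The collection rules are in Section 1.2 and Section 8.2:

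- **Footnote e** lists blood pressure, heart rate, respiratory rate and temperature at Screening, before the first dose, at Hours 0 to 72 and at Day 15/Early Termination. SpO2 is not on that list. The footnote adds: "Monitoring of continuous pulse oximetry begins at Hour 0 (start of the domiciling period".
- **Footnote n** says: "Subjects will be on continuous pulse oximetry monitoring throughout the confinement period but, absent a respiratory AE, oxygen saturation" "will be recorded every 12 hours post-end of surgery".
- **Section 8.2** likewise describes SpO2 "checks every 12 hours post-end of surgery", with a ±10-minute window.
- **The Schedule row** "Continuous Pulse Oximetry" carries six marks. By column position they sit at Hours 12, 24, 36, 48, 60 and 72. None is at Screening, Pre-Surgery, Hours 0 to 8 or Day 15.

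Other text points the other way. Sections 1.1 and 8.2, like Section 3, count continuous pulse oximetry as a vital sign. The synopsis includes it in the early-termination assessments, whereas footnote v does not.

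Section 4.2 puts Tmax of naproxen and pregabalin after XG005 "at approximately 4 hours".

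**The concern.** A change-from-baseline endpoint needs a value before exposure. A per-dose endpoint needs at least one value after each dose, and a follow-up comparison needs a value at follow-up. Read as written, the schedule supplies none of these for SpO2 except values after the later doses.

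Hour 0 could not stand in as a baseline. It follows dose 1, propofol, fentanyl and possibly midazolam (Section 6.5.5), and no SpO2 record is marked there.

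The timing of the values that are recorded also matters. Dosing is 12-hourly from dose 1 and SpO2 recording is 12-hourly from last suture, so the two clocks run in step. Records after later doses fall at nearly the same post-dose time, ahead of the expected peak. A by-arm table showing no SpO2 difference could then reflect when values were written down. Dizziness and somnolence were the most common events in the Phase 1 tablet study (Section 2.3), and subjects here also receive sedation and an opioid, so SpO2 is a result that readers of the safety section will look for.

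**Working it through.** The plan gives no figure of its own to reproduce here; the check is clock arithmetic.

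**Inputs**

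- Dose 1 is 60 minutes before surgery, then dosing is every 12 h from dose 1 (Section 1.2 footnote k; Section 6.2).
- Surgery lasts at most 90 minutes (Section 6.5.5). No minimum is given, so duration D is taken as 0 to 1.5 h.
- SpO2 records are at 12, 24, 36, 48, 60 and 72 h after last suture.
- Tmax is about 4 h (Section 4.2).

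**Step 1: last suture.** Time after dose 1 = 1 h + D = 1.0 to 2.5 h.

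**Step 2: each record.** Record k (k = 1 to 6) falls 12k + (1.0 to 2.5) h after dose 1. Dose k+1 is at 12k h, so where that dose is given the record is 1.0 to 2.5 h after it.

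| Record | Hours after dose 1 | Preceding dose | Hours after that dose |
|---|---|---|---|
| Hour 12 | 13.0–14.5 | dose 2 (12 h) | 1.0–2.5 |
| Hour 24 | 25.0–26.5 | dose 3 (24 h) | 1.0–2.5 |
| Hour 36 | 37.0–38.5 | dose 4 (36 h) | 1.0–2.5 |
| Hour 48 | 49.0–50.5 | dose 5 (48 h) | 1.0–2.5 |
| Hour 60 | 61.0–62.5 | dose 6 (60 h) | 1.0–2.5 |
| Hour 72 | 73.0–74.5 | dose 6 (60 h) if dosing ends there; dose 7 if one is given at 72 h | 13.0–14.5, or 1.0–2.5 |

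The text does not settle whether a dose is given at 72 h, so both cases are shown.

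**Step 3: dose 1.** No record falls in the 0 to 12 h interval. The dose-1 peak, 4 h post-dose, is 4 − (1.0 to 2.5) = 1.5 to 3.0 h after last suture and passes without a scheduled SpO2 record.

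**Step 4: distance from the peak.** Records at 1.0 to 2.5 h are 1.5 to 3.0 h before 4 h.

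**Step 5: windows.** The first dose may be ±10 minutes (Section 1.1), and later doses and SpO2 checks ±10 minutes each. The latest case is 70 + 90 + 10 + 10 = 180 minutes = 3.0 h post-dose. The earliest, with D = 0, is 50 + 0 − 10 − 10 = 30 minutes = 0.5 h.

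**Step 6: the existing vital-signs times.** Assuming surgery of 30 to 90 minutes, last suture is 1.5 to 2.5 h after dose 1, so Hour 2 is 3.5 to 4.5 h after dose 1. A vital-signs set is therefore already taken around the dose-1 peak, without SpO2.

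**Counts on the operative schedule.** Pre-dose SpO2 values: 0. Values in the dose-1 interval: 0. Values at the scheduled Day 15 visit: 0.

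**The case against.** **Oximetry is a vital sign, so it is taken pre-dose and at Day 15.** Section 3 itself, with Sections 1.1 and 8.2, supports this, and the Vital Signs row is marked at Screening, Pre-Surgery and Day 15. Footnote n also ties monitoring to the confinement period, which Section 4.1 starts at check-in. A reader might infer from the schedule that the endpoint certainly cannot be computed, but the documents do not go that far, because one reading would supply a baseline. Against that reading stand footnote e's explicit list, its Hour 0 start and the unmarked Schedule cells. The text conflicts, and sites could follow it differently.

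**Subjects are monitored continuously.** This stands. Oximetry runs from Hour 0, a respiratory AE can prompt further records, and clinically significant findings become AEs (Section 8.2). Respiratory rate and Ramsay scores are taken densely in the early hours. The inference that subjects are unobserved at the dose-1 peak is not supported. What is thin is the recorded SpO2 data.

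**The endpoint is descriptive.** Also true. The synopsis names SpO2 without a baseline or per-dose requirement, randomised arms can be compared at each time point without a baseline, and detail is deferred to a separate SAP. But Section 3 promises change from Baseline, and an SAP cannot supply values that were not recorded.

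**The fixed one-hour offset is disputed.** Section 4.1 has surgery within 60 minutes of the first dose. That must be reconciled with the other sections, but a shorter lead moves every record earlier and so further from 4 h.

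**Conclusion.** The point holds as a mismatch between a stated endpoint and its data collection, made worse by conflicting text. If sites follow footnotes e and n and the Schedule row, there is no SpO2 baseline, no value after dose 1 until dose 2 has been given, and no Day 15 value. Records after later doses are nominally 1.0–2.5 h post-dose, and at most 3.0 h with every window stacked, which is before the stated Tmax of about 4 h.

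Three stronger inferences should be resisted:

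- It is not certain that every record shares this early timing. If dosing ends at 60 h, the Hour 72 record is 13.0–14.5 h after the last dose.
- No dose-related CNS effect is claimed. Section 2.3 reports no dose- or treatment-related trend in TEAE incidence in the first two Phase 1 studies.
- The absence of a Day 15 value refers to the scheduled visit. At early termination the synopsis would give a reading and footnote v would not.

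The result assumes a 60-minute lead and surgery of 0 to 90 minutes, and counts scheduled records only. The primary efficacy analysis is unaffected. The change is worth making because a pre-dose value that was not recorded cannot be recovered later.

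**What to change.** In footnotes e and n, the oximetry row and Section 8.2, record SpO2 with every existing vital-signs set: Screening, pre-dose on Day 1, Hours 0, 1, 2, 4, 8, 12, 24, 36, 48, 60 and 72, and Day 15/Early Termination. Define the pre-dose Day 1 value as the SpO2 baseline. Then bring Section 1.1 (assessments and early-termination list), the Schedule row, footnotes e, n and v, Section 3 and Section 8.2 to one statement of whether SpO2 belongs to the vital signs and when it is recorded.

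This supplies the baseline and follow-up values and covers the dose-1 peak through Hour 2. It does not reach the peaks of later doses. Adding SpO2 at the between-dose pain and sedation assessments would not reach them either. With surgery of 30 to 90 minutes, Hour 16 is 16 + (1.5 to 2.5) − 12 = 5.5–6.5 h after dose 2, Hour 20 is 9.5–10.5 h after dose 2, and Hours 30, 42, 54 and 66 are each 7.5–8.5 h after the preceding dose. Those readings are therefore not proposed.

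The cost is edits to the schedule text, one eCRF field and a few more recorded values per subject, at visits where staff already take vital signs.
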